6.14.4. Vital Signs and Other Physical Findings

As described more fully in compound level safety standards and in the vital signs-related PhUSE white papers (PhUSE 2013; PhUSE 2015), vital signs will be summarized similarly to the clinical laboratory evaluation (see Section 6.14.4). For vital signs, the low and high limits are based on a combination of a specified value and a change or percentage change as defined in the compound level safety standards. In this case, the PhUSE white paper recommends providing scatter plots and shifts to low/high. Boxplots will also be presented.

6.14.5. Electrocardiograms

Complete electrocardiogram (ECG) data will not be part of the clinical database. Any clinically significant findings from ECGs that result in a diagnosis and that occur after the patient receives the first dose of the investigational treatment will be reported as an AE via eCRF. Aside from standard AE summary tables no additional analysis of ECG data will be performed.

6.14.6. Immunogenicity

An individual sample is potentially examined multiple times in a hierarchical procedure to produce a sample antidrug antibodies (ADA) assay result and potentially a sample neutralizing antidrug antibodies (NAb) assay result. A patient has treatment-emergent antidrug antibodies (TE-ADA) when ADAs are induced or boosted by exposure to study drug; that is, when at least 1 postbaseline ADA sample has a 4-fold increase in titer compared to baseline (if ADAs were present at baseline) or has a titer 2-fold greater than the minimum required dilution of 1:10 (if no ADAs were present at baseline).

Compound level safety standards will be followed in the analyses of immunogenicity. Listings of immunogenicity assessments will be provided-along with the summary of specified TEAEs by TE-ADA status. The summary of TE-ADA and NAb status will be produced for the 2 safety populations, where the postbaseline period for reporting is the same as described for AEs in Section 6.14.2. The subgroup analysis of efficacy by TE-ADA status (positive, negative) is described in the Section 6.15. Additional assessments of the relationship between immunogenicity and efficacy will be performed as part of the integrated analysis including other Phase 3 mirikizumab psoriasis trials.

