
To assess efficacy of 250-mg mirikizumab Q8W and 125-mg mirikizumab Q8W as compared to secukinumab with respect to clinical response
	
At Week 52 and at various time points during the Maintenance Dosing Period:
 
 • Proportion of patients achieving PASI 90 • Proportion of patients achieving a DLQI total score of (0,1) with at least a 5-point improvement (reduction) from baseline in patients with a baseline DLQI total score ≥ 5 • Proportion of patients achieving DLQI (0,1) with DLQI baseline score >1

Evaluate the pharmacokinetics and pharmacokinetic/pharmacodynamic relationship of mirikizumab
	
 • Clearance and volume of distribution of mirikizumab • Relationship between mirikizumab exposure and efficacy (sPGA and PASI)

Exploratory
 
To evaluate the potential development of antimirikizumab antibodies and their potential relationship with efficacy, TEAEs, and mirikizumab exposure
	
At Week 16 and Week 52:
 
 • Relationship between TE-ADA and efficacy (sPGA and PASI) • Relationship between TE-ADA and TEAEs • Relationship between TE-ADA and mirikizumab pharmacokinetics

Protocol-Defined Objectives and Endpoints

Abbreviations: BSA = body surface area; DLQI = Dermatology Life Quality Index; MCS = mental component summary; NAPSI = Nail Psoriasis Severity Index; PASI = Psoriasis Area and Severity Index; PASI 75/90/100 = $\geq 75\%$ / $\geq 90\%$ / $\geq 100\%$ improvement in PASI from baseline; PatGA = Patient's Global Assessment of Psoriasis; PCS = physical component summary; PPASI = Palmoplantar Psoriasis Severity Index; PSS = Psoriasis Symptoms Scale; PSSI = Psoriasis Scalp Severity Index; Q8W = every 8 weeks; QIDS-SR16 = 16-item Quick Inventory of Depressive Symptomatology; SF-36 = Short Form 36-item Health Survey; sPGA = static Physician's Global Assessment; TE-ADA = treatment-emergent antidrug antibody; TEAE = treatment-emergent adverse event; WPAI PSO = Work Productivity Activity Impairment Questionnaire – Psoriasis.

- a All primary and major secondary endpoint analyses will utilize the multiplicity control technique called “graphical multiple testing procedure” to control the overall family-wise Type I error rate.

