5.1.3. Blinded Maintenance Period (Week 16 to Week 52 [36 Weeks])

Patients who were randomly assigned at baseline to receive mirikizumab in the Blinded Induction Period were also randomly assigned to receive either 250-mg mirikizumab every 8 weeks (Q8W) SC or 125-mg mirikizumab Q8W SC in the Blinded Maintenance Period, with maintenance dosing starting at Week 16 and ending at Week 48. Patients who were randomized to placebo in the Blinded Induction Period will receive 250-mg mirikizumab SC every 4 weeks (Q4W) for Weeks 16 through 32 and 250-mg mirikizumab Q8W thereafter. Patients who were randomized to 300-mg secukinumab SC in the Blinded Induction Period will continue this treatment with Q4W dosing during the Blinded Maintenance Period, starting at Week 16 and ending at Week 48.

Throughout the study, patients will receive placebo, as appropriate, to maintain the study blind across treatment groups.

A discontinuation criterion has been included for patients in any treatment group who remain at or above their baseline static Physician's Global Assessment (sPGA) score at Week 16 (Visit 9) and Week 24 (Visit 11), or remain at or above their baseline Psoriasis Area and Severity Index

(PASI) score at Week 16 (Visit 9) and Week 24 (Visit 11), to ensure patients who have not shown any benefit from study treatment are offered alternative therapies.

At Week 52, patients have 1 of the following options:

- Enter Study I6T-MC-AMAH (AMAH), a long-term extension study in which patients receive 250-mg mirikizumab Q8W SC or 125-mg mirikizumab Q8W SC, OR
- Discontinue study treatment and complete Study AMAJ's 12-week Posttreatment Follow-Up Period.

[figure not shown]
Patients who discontinue early from the study for any reason during this period will stop treatment and continue to the ETV and then the 12-week Posttreatment Follow-Up Period.

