6.14.2. Adverse Events

A treatment-emergent adverse event (TEAE) is defined as an event that first occurred or worsened in severity after baseline. The MedDRA Lowest Level Term (LLT) will be used in the treatment-emergent computation. The maximum severity for each LLT during the baseline period will be used as baseline. The treatment period will be included as postbaseline for the analysis. For events with a missing severity during the baseline period, it will be treated as ‘mild’ in severity for determining treatment-emergence. Events with a missing severity during the postbaseline period will be treated as ‘severe’ and treatment-emergence will be determined by comparing to baseline severity. For events occurring on the day of first taking study medication, the start times of the study treatment and AE will be used to determine whether the event was pre- versus posttreatment. If start time for the AE is missing, it will be assumed to have started in the later period.

Summary tables as described in [Table AMAJ.6.7](#) will be presented for the 2 safety populations/periods as indicated. Summary tables will include the number and percentage of patients reporting an event. For events that are gender-specific (as defined by MedDRA), the number of participants at risk will include only patients from the given gender. Comparisons will be performed using Fisher’s exact test. For document writing purposes, tests with 2-sided p-values less than 0.05 will be referred to as “having strong evidence for a treatment difference”, unless otherwise noted. However, p-values should not be over interpreted for these safety analyses. Except for prespecified hypotheses, they correspond to data-driven hypotheses and hence are only useful as a flagging mechanism.

For the 2 safety populations, the baseline period and postbaseline will be defined as follows:

- *Induction Safety Population*: The baseline period is the Screening Period. The postbaseline period will be the Induction Period.
- *All Active Treatment Safety Population*: The baseline period for patients randomized to mirikizumab and secukinumab during induction is the Screening Period. For patients randomized to placebo, the baseline events are those events which are ongoing at the time of the first injection with mirikizumab (that is, the baseline period is a moment in time). Two different postbaseline periods will be used:
 - For “all miri” and “all secu”, the All Active Treatment Periods will be used.

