6.15. Subgroup Analyses

6.15.1. Efficacy Subgroup Analyses

Subgroup analyses will be conducted for the primary endpoints of Week 16 PASI 90 and sPGA (0,1) proportion in the ITT Population. Also, subgroup analysis for the Week 52 PASI 90 and sPGA (0,1) proportion in the ITT population will be performed. The subgroups to be analyzed are listed in [Table AMAJ.6.4](#) along with the demographic characteristics. Some additional subgroup analyses may be performed to meet regulatory requirements in specific countries. Additional subgroup analyses, which are not based on baseline/demographic characteristics in [Table AMAJ.6.4](#) are:

- concomitant topical steroid product use: yes, no.
- concomitant systemic corticosteroid use: yes, no
- treatment-emergent antimirikizumab antibody status: positive, negative

The analysis of additional subgroups will not require an amendment to the SAP. Missing outcome data will be imputed using NRI. Within each subgroup category the proportion of responders by treatment, treatment differences and 95% CIs will be displayed. Also, p-values using Fisher's exact test for treatment comparison will be provided. If the number of patients in any subgroup category is <10% of the total population, only summaries of the efficacy data will be provided (that is, no inferential testing). Forest plots will be generated to display the odds ratios and 95% CIs for the efficacy subgroup analyses.

A logistic regression model with treatment, subgroup, and the interaction of subgroup by treatment will be used. The subgroup-by-treatment interaction will be tested using the Firth correction (Firth 1993) at the significance level of 0.10.

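### SAP 6.14.6 tabulates adverse events by ever/never antibody status and states no rule on whether the event preceded the antibody, so a real antibody-related increase would be understated

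*SAP*

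**What the plan says.** SAP 6.14.6 (Immunogenicity) classes a patient as TE-ADA positive if antibodies were present at baseline and "when at least 1 postbaseline ADA sample has a 4-fold increase in titer compared to baseline", or, if none were present at baseline, if a postbaseline sample passes a titer threshold. One qualifying sample at any time is enough. The same section plans "Listings of immunogenicity assessments will be provided-along with the summary of specified TEAEs by TE-ADA status". It also says "Compound level safety standards will be followed in the analyses of immunogenicity", and for the TE-ADA summaries it fixes the window: "where the postbaseline period for reporting is the same as described for AEs in Section 6.14.2".

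SAP 6.14.2 (Adverse Events) times events against baseline only: "A treatment-emergent adverse event (TEAE) is defined as an event that first occurred or worsened in severity after baseline". SAP 6.15.1, for the efficacy subgroup, gives the levels as "treatment-emergent antimirikizumab antibody status: positive, negative", with no time-varying form.

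The table serves an exploratory endpoint in SAP Table AMAJ.4.1, "Relationship between TE-ADA and TEAEs", listed for Week 16 and Week 52. For immunogenicity, the note to Table AMAJ.6.2 drops the secukinumab arm and combines the active-treatment and active-treatment-plus-follow-up outputs.

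**The concern.** Antibody status develops during treatment, so it is a time-dependent exposure. Grouping patients by whether they ever became positive treats it as known at the first dose. Two things follow.

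- An event before seroconversion cannot have been caused by the antibody, yet it counts in the positive group. This pulls any real difference towards none.
- A patient whose event ends treatment may have fewer antibody samples and less time to seroconvert. Such patients tend to stay in the negative group, which lowers the apparent risk in positives.

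The contrast is within mirikizumab-treated patients and is not randomised. This summary and the accompanying listings are the only analysis that the SAP describes for the TE-ADA/TEAE endpoint. The integrated work mentioned in 6.14.6 concerns efficacy. At stake is whether an immunogenicity-related harm is seen at its true size.

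**Working it through.** **Nothing to reproduce.** The documents give no TE-ADA incidence, no event rate by antibody status and no antibody sampling schedule. Every figure below rests on stated assumptions.

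**Hand calculation.** Let f be the average share of the observation window that passes before antibody onset in positive patients, HR the true hazard ratio after onset, and q the share of events that end follow-up and sampling. For uncommon events and equal follow-up:

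- ever/never risk ratio ≈ (1 − q) × f + (1 − f) × HR
- with q = 0, share of positive patients' events that precede the antibody ≈ f / [f + (1 − f) × HR]

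The first formula moves the pre-antibody events that stop sampling out of the positive group. It ignores the small rise this causes in the negative group. Assume f = 0.5 (onset spread evenly over the window):

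- HR 1: q = 0 gives 0.5 + 0.5 = 1.0; q = 0.5 gives 0.25 + 0.5 = 0.75; q = 1 gives 0.5
- HR 2: q = 0 gives 0.5 + 1.0 = 1.5; q = 0.5 gives 0.25 + 1.0 = 1.25; q = 1 gives 1.0
- HR 3: q = 0 gives 0.5 + 1.5 = 2.0; q = 0.5 gives 0.25 + 1.5 = 1.75; q = 1 gives 1.5
- Share of events before the antibody at q = 0: 0.5/1.0 = 50% for HR 1, 0.5/1.5 = 33% for HR 2, 0.5/2.0 = 25% for HR 3

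**Simulation.** Assumptions: exponential antibody onset with 10–30% positive by Week 52; 5–15% with the event by Week 52 without antibody; background dropout 0–20%; samples at Weeks 4, 8, 12, 16, 24, 36 and 52, with or without an early termination sample; and a variant that counts 12 weeks of follow-up.

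| True HR | Ever/never risk ratio, q = 0 | q = 0.5 | q = 1 | Rate ratio with time split at the antibody |
|---|---|---|---|---|
| 1 | 1.00–1.11 | 0.65–0.84 | 0.37–0.66 | 0.96–1.03 |
| 2 | 1.47–1.67 | 1.07–1.31 | 0.69–1.01 | 1.92–2.02 |
| 3 | 1.87–2.25 | 1.40–1.81 | 1.00–1.59 | 2.77–3.02 |

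Each hand-calculated value lies within the matching range. At HR 1 and q = 0.25 the ratio is 0.90–0.92. At HR 1 and q = 0, 47–51% of positive patients' events precede antibody onset. Values slightly above 1 in the first cell arise because patients followed for longer have more chance both of an event and of a positive sample. Counting the 12 weeks of follow-up gives the mildest null bias: 0.84 at q = 0.5 and 0.66 at q = 1.

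A second set of assumptions (TE-ADA in 10–40%, onset uniform over Weeks 3–28, 6–8% with the event, 10% dropout, 0 or 30% stopping after the event) gives 0.81–1.08 for HR 1, 1.30–1.72 for HR 2 and 1.66–2.35 for HR 3. Between 20% and 59% of positive patients' events then fall before the first positive sample.

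**How many events to expect.** SAP 5.2 plans 888 mirikizumab and 111 placebo patients, and the latter switch to mirikizumab at Week 16: 888 + 111 = 999. On the second set of assumptions with no effect:

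- 10% TE-ADA: about 100 positives, 6–8 with an event. After the antibody, 6 × (1 − 0.59) ≈ 2 to 8 × (1 − 0.20) ≈ 6.
- 40% TE-ADA: about 400 positives, 24–32 with an event. After the antibody, 24 × 0.41 ≈ 10 to 32 × 0.80 ≈ 26.

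**The case against.** **The rule may exist elsewhere.** SAP 6.14.6 defers to the compound level safety standards, so a reader who infers that the sponsor ignores event order altogether goes beyond the text. This objection stands. What can be said is that the SAP itself states no rule.

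**Early stoppers are not simply counted as negative.** A reader might infer that they are, but the SAP does not say so. In maintenance, "Patients who discontinue early from the study for any reason during this period will stop treatment and continue to the ETV", and the 12-week follow-up comes after that. The immunogenicity outputs combine treatment and follow-up. If samples are taken then, a stopper can still become positive. This also stands: it softens the bias in the simulation but does not remove it.

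**A false protective look is not general.** A reader might infer that antibodies with no effect would usually appear protective. That appearance needs events that shorten antibody sampling. Without them the null ratio is 1.00–1.11.

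**The table is descriptive.** Only specified events are summarised, for an exploratory endpoint, with no model or decision rule for this table. SAP 6.14.2 treats safety p-values outside prespecified hypotheses as flags. Listings of immunogenicity assessments and of serious events are planned, and hypersensitivity events are timed against dosing, so sequence can be examined case by case. All true, and it limits the importance of the point. Listings do not replace a prespecified rule for the summary.

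**A mandatory Cox model is too much.** With perhaps 2 to 6 post-antibody events at the low end, it would say little. This stands, and the fix makes the model conditional.

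**Conclusion.** The point holds in a limited form. The SAP text groups events by ever/never TE-ADA status and gives no ordering rule. If it is followed as written, a real antibody-related increase is understated. A true hazard ratio of 2 shows as roughly 1.1 to 1.7 when up to half of events end follow-up, and as 0.69–1.01 in the extreme case where all do. Dilution appeared in every scenario tried. With no effect, the ratio is about 1.0 to 1.1 and falls below 1 only when events curtail antibody sampling.

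The sizes depend on assumed antibody, event, dropout and sampling patterns. The direction of the dilution does not depend on a particular choice among them. If the compound standards already order events against the antibody, only a citation is missing.

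A reader might infer that the trial's efficacy conclusions or patient care are touched. The documents do not support that: the endpoint is exploratory, no primary or major secondary conclusion relies on it, and no dosing or stopping rule is involved.

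**What to change.** In SAP 6.14.6, for mirikizumab-treated patients evaluable for TE-ADA:

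1. Split the specified TEAEs in positive patients into onset before and onset after the first TE-ADA-positive sample.
2. Give exposure-adjusted rates from the first mirikizumab dose, with time before the first positive sample counted as antibody-negative.
3. Flag positives first detected at an event-triggered or early termination sample. If such an event is placed on the positive side, it brings almost no positive person-time with it and biases the split rate slightly upward. State how same-day cases are classed.
4. Add a Cox model with TE-ADA as a time-dependent covariate only if event numbers allow.
5. State that the ever/never table alone will not be interpreted as the TE-ADA/TEAE relationship.

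If the compound level safety standards already do this, cite the exact rule instead.

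The cost is SAP wording and one extra table, from event onset and sample dates. The downside is precision: antibody onset is known only to the sampling interval, and few events will give wide intervals.

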6.14.7. Special Safety Topics including Adverse Events of Special Interest

This section includes areas of interest whether due to observed safety findings, potential findings based on drug class, or safety topics anticipated to be requested by a regulatory agency for any reason. In general, potential adverse events of special interest (AESI) relevant to these special

safety topics will be identified by one or more standardized MedDRA query(ies) (SMQs), by a Lilly defined MedDRA PT listing based upon the review of the most current version of MedDRA, or by treatment-emergent relevant laboratory changes, as described below. Additional special safety topics may be added as warranted.

Unless otherwise specified, the AESIs will be summarized for the 2 safety populations during their associated study periods using the baseline and postbaseline definitions described in Sections 6.14.2 and 6.14.3.

Full details of the search terms and rules for deriving AESIs in each of the sections below are described in the compound level safety standards along with information about the types of summaries and listings to be provided.

6.14.7.1. Hepatic Safety

Hepatic labs include alanine aminotransferase (ALT) and aspartate transaminase (AST), total bilirubin (TBL) and serum alkaline phosphatase (ALP). When criteria are met for hepatic evaluations, investigators will complete a follow-up Hepatic Safety eCRF.

Analyses will include:

- ALT and AST: The percentages of patients with a measurement greater than or equal to 3 times (3X), 5 times (5X), and 10 times (10X) the Covance upper limit of normal (ULN) during the treatment period for all patients with a postbaseline value and for subsets based on various levels of baseline value.
- TBL and ALP: The percentages of patients with a measurement greater than or equal to 2 times (2X) the Covance ULN during the treatment period will be summarized for all patients with a postbaseline value and for subsets based on various levels of baseline value.
- Plot of maximum postbaseline ALT versus maximum postbaseline TBL (Induction Safety Population for All Periods: ever on miri and never on miri).
- A listing of the information collected on the Hepatic-Safety eCRF.

6.14.7.2. Infections, including opportunistic infections and serious infections

Infections will be defined using the PTs from the MedDRA Infections and Infestations SOC. Treatment-emergent infections will be analyzed for: all infections (by maximum severity), serious infections and opportunistic infections (OI). The MedDRA terms used to identify infections considered to be OI in patients with immune mediated inflammatory conditions treated with immunomodulatory drugs are based on Winthrop et al. (2015) and are listed in the compound level safety standards. The list contains narrow (more specific) and broad (less specific) PTs with respect to these prospectively defined OIs.

Analyses will include:

- treatment-emergent infections by PT
- serious infections by PT
- OI: treatment-emergent OI by narrow terms and broad terms separately

6.14.7.3. Hypersensitivity

Hypersensitivity reactions is used as an overarching term to describe events that are systemic or localized reactions that likely have an allergic/hypersensitivity etiology. Patients will be evaluated by the investigator for signs and symptoms suggestive of hypersensitivity and investigators will complete a follow-up eCRF designed to record additional information.

Potential hypersensitivity reactions will be determined using the following SMQs: anaphylactic reaction, hypersensitivity, and angioedema. Potential hypersensitivity will be categorized as immediate (that is, occurring within 24 hours) and non-immediate (that is, occurring after the day of study drug administration but prior to subsequent drug administration) based on the timing of the reaction.

Analyses will include:

- for immediate hypersensitivity: (1) combined narrow/algorithmic search (that is, any narrow term from any one of the SMQs, or anaphylaxis algorithm); (2) narrow search (that is, any narrow term) by SMQ; (3) broad search (that is, any narrow or broad term) by SMQ; and (4) TEAEs (occurring on the day of study drug administration) by PT not in any of the 3 SMQs
- for nonimmediate hypersensitivity: (1) combined narrow search (that is, any narrow term from any one of the SMQs); (2) narrow search (that is, any narrow term) by SMQ; and (3) broad search (that is, any narrow or broad term) by SMQ

